4.2.4 Comparison of driving performance between treatment arms

The driving simulation assessments will be conducted in the substudy. (1) Driving measurements (standard deviation of lateral deviation (SDLP) for lane tracking and coherence for car following) following 8 weeks of study medication administration will be compared between treatment arms using ANOVA, to determine whether driving skills will be different after stable cannabis treatment. Acute cannabis effects will be then tested using a covariance pattern model (e.g., unstructured model) including fixed effects of treatment arm, time (minutes), and their interaction. (2) We will also include terms for pain (separately using intensity and relief), its interaction with treatment, and time too, the latter to test for recovery of the cannabis effect back to the Hour 1 baseline level. (3) The correlation (Pearson or Spearman, as appropriate) between blood $\Delta 9$ -THC and each of SDLP and coherence will be estimated at each hour using a 95% confidence interval applied to the Fisher Z-transformation, then back-transformed. Secondary analyses will use independent t-tests or Wilcoxon rank sum tests to compare differences between the means of each of coherence and SDLP for high and low blood $\Delta 9$ -THC levels split at 7 ng/ml. (Aim 3)

4.3 Exploratory analysis:

4.3.1 We will assess the association of daily pain intensity and the dose of treatment (mean daily number of puffs or pills) using a mixed-effects model including fixed effects of dose, treatment regimen, time (i.e., day or week), and dose x treatment regimen interaction, and subject-specific random effect. A significant interaction indicates the association of the dose and pain intensity differs in the three treatment arms. Use of breakthrough pain medication will be then included in the model to remove its confounding effect if it's present. A Non-significant interaction will be removed from the models.

- 4.3.2 Cumulative distributions of maximal pain reduction from baseline among treatment groups will be compared using Kolmogorov-Smirnov tests. This test (nonparametric) will indicate if a given treatment is likely to produce more overall pain reduction than another treatment regimen and takes into account an expected delay in effects of dronabinol compared to whole plant cannabis.
- 4.3.3 To test if a treatment effect on pain may be linked to mood and neuropsychological side effects of treatment, a mechanistic analysis using the mediation model methods of Preacher and Hayes {Preacher KJ and Hayes AF: SPSS and SAS procedures for estimating indirect effects in simple mediation models, 2004, *Behavior Research Methods*, 36:717-731} will be used, allowing for multiple mediators to be tested simultaneously.

5. Sample Size and Accrual

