Cannabis Withdrawal Scale: The Cannabis Withdrawal Scale can be used as a diagnostic instrument in clinical and research settings where monitoring of withdrawal symptoms is required.²² This will be performed after the 2-week tapering period has concluded. (10 minutes) If there was a previous adverse event or events (AE(s)), the Cannabis Solicited Adverse Events instrument will again be administered to ensure that the AE(s) have resolved. Participants will continue to be followed until there is resolution of the AE(s).

ARM #2. Driving Simulation:

Subjects with drivers’ licenses will be scheduled for two experimental visits; one before they begin the randomized controlled trial, and a second visit after finishing their 8th week treatment. The initial visit will involve a 20-minute session to garner baseline values for driving skills. This visit will coincide temporally with the first session for the randomized controlled trial prior to Week 1 (Appendix 12).

At the time of the second driving simulation visit, subjects will be assigned the same medication that they have been using during the randomized controlled trial. Using a Volcano Vaporizer, subjects will inhale the average number of puffs they had consumed per session throughout the four previous weeks of the randomized controlled trial. They will use the Vaporizer before Hour 2 and again before Hour 6 (Table 3). They will also take the same oral medication that was provided during the randomized controlled trial. In addition to examining the effects on driving simulation, acute effects of study medications on spontaneous pain and vital signs will be determined (Appendix 13). We will administer the simulator sickness assessment during the first 2 hours of the appointment to ensure that the participant is physically able to perform the driving simulation tasks.

At the beginning of driving simulation appointments, participants will be given a urine toxicology and a breathalyzer test to test for any illicit substances that is not prescribed by a physician. Should the participant screen positive for an illicit substance, they will either be asked to reschedule or be discontinued from the study at the Principal Investigator's discretion. If this happens, participants will be compensated \$10 for arriving to the scheduled appointment.

During the Driving Simulation study visit, the participants will be given paper and pencil forms that measure the following:

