- **Task 1: Lane Tracking/Divided attention:** Participants will be instructed to maintain their lane position and speed, and respond to divided attention stimuli in the two corners of the monitor. The primary outcomes are standard deviation of lateral deviation (SDLP), latency and accuracy on the divided attention tasks, and speed deviation. SDLP is a measure of how well subjects maintain their lane position, providing an index for each subject's road tracking error and ability to control the lateral motion of the car. It is primarily controlled by automatic information processing and outside of conscious control. SDLP has been shown to be sensitive to the effects of medications in both on-road and simulator studies (23-27). It has been examined in individuals under the influence of alcohol, marijuana, and MDMA, as well as with neurologic populations (28-32). SDLP has also demonstrated good test-retest reliability over short and long-term follow-ups (33-36). (7 minutes)
- **Task 2: Car Following:** The primary outcomes are (1) coherence between the participant and lead cars (a general correlation [0–1] of the participant's ability to accurately track the speed variations of the lead car); (2) time delay (or the reaction time to changes in the lead car's speed); and 3) distance from the lead car (7 minutes)
- **Task 3: Multi-tasking (Surrogate Reference Task [SuRT]):** The primary outcomes are response latency and accuracy on the SuRT tasks. In addition, we will examine SDLP and speed deviation during this more challenging divided attention task. The SuRT is a visual

perceptual task which presents subjects with an approximately 8" touch screen filled with circles and requires participants to point to a target circle.

Figure 1. Surrogate Reference Task (SuRT)

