4.2 Secondary endpoints

The secondary outcomes include the level of use of breakthrough pain medication, pain tolerance and sensitivity, chronic low back pain (CLBP) impact score, neuropathic pain scale (NPS, a sum of 10 pain descriptors), profile of mood states (total mood disturbance scores), Beck Depression Inventory II, ability to learn and recall measured using Hopkins Verbal Learning Test (HVLT), measures of concentration, psychomotor speed, and graphomotor abilities by Wechsler Adult Intelligence Scale -III (WAIS-III) digit symbol test, marijuana subscale (M-scale), motor coordination and speed evaluated by grooved pegboard test. In addition, subjective and psychoactive side effects (e.g., good drug effect, drug high) and measures (e.g., lane tracking, car following) in driving simulation will be examined as secondary outcomes in a substudy, where completers with a valid driver's license will receive acute administration of treatment at the driving simulation visit.

All comparisons of secondary outcomes between arms will be with an order of importance as described above for the primary endpoint: 1) primary comparison: arm A vs. arm B; 2) secondary comparison: arm A vs. arm C; exploratory comparison: arm B vs. arm C. No correction will be done for multiple comparisons.

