4.2.1 Comparison of outcomes measured at 6 visits between treatment arms

The similar analysis strategies as described above for primary endpoint will be used for the secondary outcomes measured at 6 visits. Briefly, the interaction effect of treatment arm and time (6 visits) on outcome will be tested using a covariance pattern model (e.g., unstructured model). Average change at the treatment period (weeks 5-8) from baseline will be compared between the groups. Non-significant interaction terms will be removed from the models (Aim 2).

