5.1 Power Estimation

Power estimates for each outcome assumed a 5% significance level. Totally, N=120 subjects will be randomized in 1:1:1 ratio to the three treatment arms, that is, 40 subjects to each arm. Using the same 16% drop-out rate experienced in our previous study and that 87% of the completers possess a valid driver's license, a national average published by the Department of Transportation, power was calculated for 33 subjects per treatment arm (total N=99) for Aims 1 and 2, and 29 subjects per treatment arm (total N=87) for Aim 3. We have 80% power to detect effect sizes equivalent to Cohen's $d=0.54$ and $d=0.58$ for sample sizes 33 and 29 respectively. This effect size is based on differences between groups of changes from baseline at the end of the study (week 8). The power is calculated using specific formulas for a time-by-treatment interaction in a longitudinal linear mixed-effects model {Diggle PJ, Heagerty P, Liang KY, Zeger SL: Analysis of Longitudinal Data, 2nd edition, 2002, Oxford University Press, Oxford, p.29}. Power is expected to be higher for larger effect sizes and fewer dropouts.

6. Data and Safety Monitoring Committee (DSMC)

Progress reports will be presented to the DSMC every 6 months. Two reports (open and closed reports) will be generated and presented in two sessions.

Key study personnel and all DSMC members will attend the open session; *the open report* will present data in aggregate form (not by arm). Open session attendees will review presented summarized data for data completeness and accuracy (e.g., review ranges for numeric variables to catch any outliers/unusual observations).

The closed session will include only the study statistician and members of the DSMC; *the closed report* will present data by treatment arm, but in blinded fashion,

i.e., arms will be presented as arm X, arm Y, arm Z. Treatment labels can be revealed to the DSMC members upon their request if major concerns arise. Statistical comparison of relevant characteristics between the arms will be done. No interim analysis comparing primary outcomes between the arms will be performed in order to preserve the power of the primary analysis and the overall Type I error at 0.05 level till the end of the study, unless requested by the DSMC. Members of the DSMC will be asked to maintain confidentiality related to the interim data presented in the closed report until the end of the trial.

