6.2 The information included in closed report

The data will be presented by blinded arms (arm X, arm Y, and arm Z), except for a notice of aggregate. The measures will be tabulated and summarized in aggregate form or by treatment arm using Mean (SD), N (%), and Median (IQR), as appropriate. The items with an asterisk (*) will be compared between arms. Kruskal-Wallis test and Fisher's Exact test will be used to compare numeric and categorical variables, respectively.

- A. *Outline of the study design:* 1) aims, 2) design summary, 3) database freezing date, 4) confidentiality statement
- B. *Enrollment and study status:* the number of 1) screened subjects (aggregate); 2) exclusion and the reasons (aggregate); 3) enrolled subjects and projected enrollment (graph of enrollment by month) (aggregate); 4) subjects completing the entire study; 5) *withdrawal from the study and the reasons; 6) missing visit(s) and the reasons.
- C. *Demographic characteristics of the cohort:* 1) age, 2) sex, 3) education, 4) Race
- D. *Baseline study relevant characteristics of the cohort*:* 1) baseline of pain intensity; 2) baseline levels of the driving performance
- E. *Baseline lab characteristics:* vital signs, e.g. heart rate and blood pressure
- F. *Safety data and study-related adverse events:* 1) type and severity (grade) of adverse events*; 2) number of adverse events; 3) number of subjects with adverse events*; 4) number of deaths related to adverse events*; 5) unanticipated problems.
- G. Protocol deviations
- H. Summary of the overall study status (closed report only)

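### The week-8 driving ANOVA ignores the pre-treatment driving session, and the Aim 3 power is stated for a change-from-baseline analysis that this test is not

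*SAP*

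**What the plan says.** Protocol section 9 (Arm #2, Driving Simulation) schedules two driving visits, one before the randomised trial begins and one after the eighth week of treatment. Of the first it says: "The initial visit will involve a 20-minute session to garner baseline values for driving skills".

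SAP 4.2.4 states that the driving measures following 8 weeks of study medication (SDLP for lane tracking, coherence for car following) "will be compared between treatment arms using ANOVA, to determine whether driving skills will be different after stable cannabis treatment". It names no covariate and no change score. The acute model that follows refers to a baseline, but that is Hour 1 of the week-8 visit, after eight weeks on treatment.

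No other outcome analysis uses the pre-treatment driving value. The modelling strategy of SAP 4.2.1, which includes change from baseline, "will be used for the secondary outcomes measured at 6 visits"; driving is not among these. SAP 6.1 and 6.2 list "baseline levels of the driving performance", but only for the monitoring committee's reports.

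SAP 5.1 gives one power statement for all aims: 80% power for d=0.54 at 33 per arm (Aims 1 and 2) and d=0.58 at 29 per arm (Aim 3). It adds: "This effect size is based on differences between groups of changes from baseline at the end of the study (week 8". The stated method is a formula for a time-by-treatment interaction in a longitudinal mixed model.

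**The concern.** Two things follow if the text is applied as written.

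First, people differ in driving skill before any treatment. In a comparison of week-8 values alone, those stable differences stay in the error term, although the design collects the measurement that could remove part of them.

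Second, the only power figure for Aim 3 belongs to a different kind of analysis. The week-8 ANOVA uses one time point and no baseline, so it is neither a change analysis nor longitudinal. A reader could take the 80% as applying to it.

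A lesser point is that the driving substudy is restricted: "completers with a valid driver's license will receive acute administration of treatment at the driving simulation visit". Completion is decided after randomisation, so the arms as analysed may differ in baseline driving more than randomised groups would. Adjustment would correct imbalance in measured baseline driving, but not all selection.

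The concern is limited to this ANOVA. The acute arm-by-time contrasts are within person and already remove stable driving skill.

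**Working it through.** **Inputs from SAP 5.1.** n=29 per arm (87 in total), d=0.58, 80% power. On alpha: "Power estimates for each outcome assumed a 5% significance level". Sidedness is not stated; two-sided is assumed.

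**Assumed.** The correlation r between pre-treatment and week-8 driving values is not given anywhere. The protocol says only that "SDLP has also demonstrated good test-retest reliability over short and long-term follow-ups", without a figure, and says nothing of the kind for coherence. I show r = 0.3, 0.5, 0.6 and 0.7.

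**Step 1: reproduce the plan's figure.** For a difference in slopes, n per arm = 2(z_α+z_β)²σ²(1−ρ)/(Sxx·slope²), with d = 8·slope/σ. Hence d = 8(z_α+z_β)√[2(1−ρ)/(n·Sxx)]. The pain schedule in SAP 4.1.1 (weeks 0, 1, 3, 5, 7, 8; mean 4) gives Sxx = 16+9+1+1+9+16 = 52. With z_α+z_β = 1.960+0.842 = 2.802 and an assumed ρ=0.5:

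- n=33: d = 8 × 2.802 × √[1/(33×52)] = 0.541
- n=29: d = 8 × 2.802 × √[1/(29×52)] = 0.577

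These match 0.54 and 0.58. The schedule and ρ=0.5 are inferred. A two-visit change score with ρ of about 0.69 fits equally well: (0.58/0.736)² = 0.621 = 2(1−ρ). Without a within-subject correlation the figures do not come out: 2.802 × √(2/29) = 0.736, not 0.58. So the stated power relies on repeated measurements within a person, which the week-8 ANOVA does not use.

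**Step 2: power of the planned test and of ANCOVA.** Pairwise contrast, noncentral t, noncentrality (d/k)·√(29/2). For ANOVA k=1 with 84 error df. For ANCOVA k=√(1−r²) with 83 error df.

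*Reading 1: d=0.58 is in SDs of the week-8 value.* ANOVA power is 58.8%, and 80% needs d=0.744.

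| r | ANCOVA power at d=0.58 | d for 80% (ANCOVA) | CI width, ANCOVA/ANOVA = √(1−r²) |
|---|---|---|---|
| 0.3 | 62.9% | 0.710 | 0.954 |
| 0.5 | 71.2% | 0.645 | 0.866 |
| 0.6 | 77.9% | 0.596 | 0.800 |
| 0.7 | 86.4% | 0.532 | 0.714 |

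ANCOVA reaches 80% at r of about 0.63. The omnibus three-arm F test, with a largest pairwise difference of 0.58, has 48% power if the third arm lies midway and 60% if it coincides with one of the other two.

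*Reading 2: d=0.58 is in SDs of change, as SAP 5.1 words it.* With equal SDs at both visits, SD(change) = σ√[2(1−r)], so the effect on the week-8 scale is 0.58·√[2(1−r)].

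| r | d on week-8 scale | ANOVA power | ANCOVA power |
|---|---|---|---|
| 0.3 | 0.686 | 73.3% | 77.3% |
| 0.5 | 0.580 | 58.8% | 71.2% |
| 0.6 | 0.519 | 49.7% | 68.5% |
| 0.7 | 0.449 | 39.4% | 65.8% |

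Here 80% is reached only for r below about 0.18 (ANOVA) or 0.21 (ANCOVA). The CI ratios are the same as under reading 1.

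**Step 3: why not a plain change score.** Its error variance is 2(1−r) times that of the week-8 value, so it beats week-8 values only when r exceeds 0.5. On reading 1 its power at r=0.3 is 45%, below the ANOVA's 59%. ANCOVA carries no such penalty beyond one degree of freedom.

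**The case against.** **The power may be meant for the acute model.** Aim 3 is worded as acute effects, and SAP 4.2.4 has a longitudinal arm-by-time model with Hour 1 as its reference. One could read the baseline in SAP 5.1, for Aim 3, as Hour 1 of the week-8 visit. But the same sentence serves Aims 1 and 2, where baseline is pre-treatment. Even if this reading is granted, the stated power still does not describe the ANOVA. What stands is that SAP 5.1 does not say which Aim 3 test it covers.

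**The gain is unknown and may be small.** This stands. No r is given. The remark on SDLP reliability has no number and does not extend to coherence. A short first session on an unfamiliar simulator, with existing cannabis users coming off their own cannabis around baseline, could lower r. At r=0.3 the gain is about 5% in CI width and four power points.

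**ANCOVA may not restore 80%.** True on reading 2 once r exceeds about 0.21. That is a reason to restate the power, not a reason to leave the baseline out.

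**The test is valid and secondary.** Also true. No bias or type I error problem is claimed, and the primary pain analysis is untouched.

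**Details are open.** SAP 4.2.4 does not say which hour of the visit enters the ANOVA, and the visible text does not say what the baseline session recorded. All four tasks take 7+7+5+5 = 24 minutes, more than the 20-minute session, so presumably not all are run in full. These affect how the fix is written, not whether it is sound.

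**Conclusion.** The concern holds. The week-8 driving comparison omits a pre-treatment value that the protocol schedules, and the Aim 3 power in SAP 5.1 does not apply to it.

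At 29 per arm and two-sided 5%, the ANOVA has about 59% power for d=0.58 if d is in week-8 SDs. If d is in SDs of change, its power falls from 73% to 39% as r goes from 0.3 to 0.7. Baseline adjustment narrows the 95% CI by about 5%, 13%, 20% and 29% at r = 0.3, 0.5, 0.6 and 0.7 on either reading. These sizes rest on the assumed r and, for reading 2, on equal SDs at the two visits. The mismatch between power statement and test does not depend on r.

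The change should be made. The consequence is lost precision and a misapplied power figure for a secondary endpoint, not an invalid analysis.

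**What to change.** In SAP 4.2.4, replace the week-8 ANOVA with an ANCOVA of each driving measure (SDLP, coherence) on treatment arm and the participant's own pre-Week-1 value of that measure, where it was recorded. Report adjusted pairwise differences with 95% CIs. In the same sentence, state which assessment of the week-8 visit is analysed and how drivers without a baseline value are handled, so that the sample does not shrink by default.

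In SAP 5.1, restate the Aim 3 power for that analysis. Give the assumed baseline correlation, whether d is in SDs of the week-8 value or of change, and which Aim 3 test the figure covers.

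Adding the covariate to the acute-effects model is optional. It sharpens overall arm differences but, with complete data, not the arm-by-time contrasts.

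The cost is a short edit in each of the two sections and one model degree of freedom. No new data are needed if the baseline session recorded SDLP and coherence. Those two tasks take 7+7 = 14 minutes and fit a 20-minute session, but the sponsor should confirm that both were recorded.

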By conducting repeat assessments for four hours following the first vaporization, we will be able to determine at what point participants no longer exhibit acute effects for each of the study medications. Participants will then complete a second vaporization and ingestion of oral medication before hour 6. We will then assess them for three hours in order to determine whether the acute effects are similar to those seen after the first vaporization, or perhaps greater (due to cumulative/residual effects). To minimize the novelty of the driving simulations, participants will complete a pretest training session to re-familiarize themselves with the hardware and the tasks that they are to encounter during the simulations. Four separate tasks will be embedded within the simulation.

Table 3 Assessments of Acute Effects One Day following 2 and 8 Weeks of Cannabis Treatment

Hour	1		2	3	4	5		6	7	8
		Vaporization/Oral Medication					Vaporization/Oral Medication			
Vital Signs	X		X	X	X	X		X	X	X
Numerical Pain Intensity Score	X		X	X	X	X		X	X	X
Cold Pressor Test	X		X					X		
Pain Relief			X	X	X	X		X	X	X
Psychoactive Effects			X	X	X	X		X	X	X
Driving Simulation	X		X	X		X		X	X	X
iPad Performance Testing	X		X	X		X		X	X	X
Blood Draw ($\Delta 9$ -THC levels)	X		X	X	X	X		X	X	X

Driving simulations: Simulation hardware will consist of a 3-screen, wide field-of-view monitor setup, steering wheel, and accelerator and brake pedals. The fully interactive simulations will assess lane tracking (standard deviation of lateral position [SDLP], or “weaving”), response to divided attention stimuli (accuracy, response time), car following, and performance during scenarios simulating routine driving as well as crash avoidance situations.

Participants in the simulator study will also be assessed for far visual acuity (Snellen Visual Acuity eye chart; need to have acuity of 20/40 or better, with or without correction), color vision, and contrast sensitivity (Vistech Contrast Sensitivity (Pelli-Robson Chart)). Participants will complete an orientation and practice drive prior to the initial simulation, in order to familiarize them with the controls and roadways.

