- **Task 4: Crash avoidance/decision-making:** In order to assess treatment effects during routine and non-routine events we will include scenarios addressing 1) the “yellow light dilemma”, wherein individuals need to respond to a yellow light onset by abruptly braking (risking a rear-end collision), or go through the intersection (risking running a red light), and 2) crash avoidance. Participants will be instructed to drive 45mph, and will encounter 8 green traffic lights, 4 of which will switch to yellow. These will be randomized within each drive. Consistent with California law (37), the yellow light phase (time before the yellow light turns red) will be 4.3s. The time available to perceive and respond to the yellow light will be held constant for all participants by controlling initiation of the yellow light by using the vehicle’s velocity to determine the time-to-location (start of intersection). This will be set at 3.4, 3.0, 2.7 and 2.2s, settings which in previous studies have shown to elicit a range of responses (running the yellow light, stopping) (38, 39). The primary outcomes will be stop/go percent and perception-reaction time (PRT; time of yellow onset to start braking or accelerating through the intersection), although a number of additional behavioral outcomes will be of interest. The simulation will also include a crash avoidance scenario in which the participant drives down a visually complex roadway (moving cars, pedestrians) and encounters the sudden appearance of a pedestrian, or car pulling out, in the roadway. Primary outcomes are the PRT to the incursion, and whether a collision occurs. Since an important aspect of this task is the unexpected nature of the event, the incursion point and object (vehicle, pedestrian) will vary across assessments (but be consistent across all participants). (5 minutes)

Performance-based tablet assessments: The following will be performed using an iPad with software designed by Digital Artefacts LLC ([name] [contact] <http://www.digitalartefacts.com>):

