4.1.1 Primary analysis

The primary analysis will be the comparison of self-reported pain intensity between arm A and arm B. An intent-to-treat analysis will be performed on data from participants who complete baseline. Data transformation (e.g., log10, square root) may be performed to improve distribution normality as appropriate. Response profiles analysis will be performed if the trend of pain intensity over time is not linear. We will compare different covariance pattern models (e.g., unstructured, compound symmetry) based on AIC and identify a covariance model with the best fit to our data. This is a randomized controlled trial so that we can remove main group effect with assumptions about equal mean responses (i.e., pain scores) at baseline for the three treatment arms. Weekly or biweekly average of pain intensity from the daily diary will be calculated as a primary outcome. Time will be treated as a factor with 6 levels (i.e., baseline, weeks 1, 3, 5, 7, 8), and the mean response profiles will be compared between the arms. The treatment effect over time will be assessed by the significance of the treatment arm x time interaction using Wald test. Also, average change at the treatment period (weeks 5-8) from baseline will be compared between the groups. (Aim 1)

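### SAP 4.2.4 tests recovery of driving against Hour 1 without a contrast, margin or confidence-interval rule, and at 29 per arm a non-significant result cannot show recovery

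*SAP*

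**What the plan says.** The protocol's lay synopsis (Section 5) gives time to recovery as the purpose of the driving simulation. Section 9, Arm #2, says of the repeat assessments after the first dose that "we will be able to determine at what point participants no longer exhibit acute effects for each of the study medications". Both are promises to conclude that an effect is absent.

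SAP 4.2.4 is the only place that names an analysis for this. It first plans a covariance pattern model for SDLP and coherence with arm, time and their interaction. It then adds pain terms and a time term, "the latter to test for recovery of the cannabis effect back to the Hour 1 baseline level". It does not say whether the comparison with Hour 1 is made within one arm or relative to placebo, how small a remaining difference counts as recovered, or what result leads to that conclusion. The 95% interval that the section does specify is for the correlation with blood THC, not for the hourly driving differences.

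Protocol Table 3 schedules drives at Hours 1, 2, 3, 5, 6, 7 and 8, with a first dose between Hours 1 and 2 and a second between Hours 5 and 6.

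**The concern.** A test against the Hour 1 level can show that driving is still impaired. It cannot show that driving has recovered, because a non-significant result is also what an imprecise estimate produces. With no margin or interval rule, an analyst who must report a recovery time has only significance or its absence to go on. If absence of significance were used, the error would run in the unsafe direction: fewer drivers give wider intervals and an earlier apparent recovery. At stake is a stated output of a secondary aim that readers may take as a statement about road safety.

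**Working it through.** **1. The sample size.** SAP 5.1 assumes 16% dropout and 87% licensed completers: 40 × 0.84 = 33.6, taken as 33; 33 × 0.87 = 28.7, taken as 29 per arm. Section 9 of the protocol makes the driving part optional and SAP 5.1 has no allowance for refusal, so 29 is a ceiling.

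**2. The plan's own power figure.** SAP 5.1 states: "We have 80% power to detect effect sizes equivalent to Cohen's $d=0.54$ and $d=0.58$ for sample sizes 33 and 29 respectively". On significance it says "Power estimates for each outcome assumed a 5% significance level", without giving sidedness; I take two-sided. On method: "The power is calculated using specific formulas for a time-by-treatment interaction in a longitudinal linear mixed-effects model". I used the visit times in SAP 4.1.1 ("baseline, weeks 1, 3, 5, 7, 8", baseline as 0). Their mean is 4 and their squared deviations sum to 16 + 9 + 1 + 1 + 9 + 16 = 52. With slope d/8 and an *assumed* within-person correlation ρ = 0.5:

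SE(d) = 8 × √[2(1 − ρ) / (n × 52)]

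- n = 33: SE = 0.193; power = Φ(0.54/0.193 − 1.96) = 79.9%
- n = 29: SE = 0.206; power = Φ(0.58/0.206 − 1.96) = 80.4%

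The stated 80% is reproduced, but only with ρ = 0.5, which the SAP does not state (at n = 29, ρ = 0.3 gives 66% and ρ = 0.7 gives 95%). What it covers matters here: "This effect size is based on differences between groups of changes from baseline at the end of the study (week 8". It is not power for recovery within a driving day, and none is given for that.

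**3. Precision of a single-hour contrast with Hour 1, n = 29, in SDs of the change.**

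- Within an arm: half-width = t(0.975, 28)/√29 = 2.048/5.385 = 0.38
- Active minus placebo: half-width = t(0.975, 56) × √(2/29) = 2.003 × 0.263 = 0.53

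If the estimate is exactly zero, the interval still reaches 0.38 or 0.53 SD of impairment. If the estimate leans towards impairment without being significant, it reaches further. With 20 per arm (illustrative), the half-widths are 2.093/√20 = 0.47 and 2.024 × √(2/20) = 0.64.

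**4. Chance of a non-significant result while impairment remains.** Noncentral t, two-sided 5%, n = 29; noncentrality δ√29 within an arm and δ√(29/2) against placebo.

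| True residual δ (SD of change) | Within arm | Versus placebo |
|---|---|---|
| 0.2 | 82% | 88% |
| 0.3 | 66% | 80% |
| 0.4 | 45% | 68% |
| 0.5 | 26% | 54% |
| 0.58 | 15% | 42% |

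As a cross-check, the SE implied by the SAP's own claim is 0.58/(1.96 + 0.84) = 0.207. It gives 69%, 51%, 32% and 20% at 0.3, 0.4, 0.5 and 0.58.

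**5. Dependence on the correlation.** The SD of a change is √[2(1 − ρ)] raw SDs. A raw residual of 0.3 SD is therefore 0.3/√[2(1 − ρ)] SDs of the change. Within an arm at n = 29 it is missed 74% of the time at ρ = 0.3, 66% at 0.5, 48% at 0.7, 31% at 0.8 and 6% at 0.9. Against placebo the last two become 57% and 29%.

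**6. What a margin rule could deliver.** Test at one-sided 2.5%, true residual zero, one hour, normal approximation. The margin with 80% power is 2.80 × √(2/29) = 0.74 SD of the change against placebo (2.80/√29 = 0.52 within an arm). A placebo-adjusted margin of 0.5 SD needs 2 × 2.80²/0.5² ≈ 63 per arm; with 29 the power is Φ(0.5/0.263 − 1.96) ≈ 48%.

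**The case against.** A reader might infer more than the documents say, and the case against those inferences is good.

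- *That recovery is judged within the same arm.* SAP 4.2.4 does not say so. The model has an arm-by-time interaction and a double-placebo arm, and the cannabis effect can naturally mean active minus placebo. On that reading, practice and fatigue common to all arms cancel, and the protocol also plans retraining before the drives. So uncorrected time trends are not an established defect. The placebo-adjusted reading does not remove the main problem, though: it widens the interval from 0.38 to 0.53 SD.
- *That non-significance will be read as recovery.* No sentence says this. What stands is that no other route to the promised conclusion is written.
- *That changing crash scenarios bias the recovery test.* Task 4 does vary by assessment: "the incursion point and object (vehicle, pedestrian) will vary across assessments (but be consistent across all participants". But SAP 4.2.4 names SDLP and coherence, not Task 4 outcomes, and scenarios shared by all participants cancel in a same-hour comparison with placebo.
- *That impairment would often be missed.* The documents give neither an expected residual nor a correlation. Section 9 cites good test-retest reliability for SDLP, so ρ of 0.8 or more is possible, and the within-arm miss rates in step 5 are then modest. The t-tests also treat each hour alone; the planned repeated-measures model may be somewhat more precise.

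Driving is also a secondary outcome in a substudy, and nothing in the documents says that the result will set driving advice.

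**Conclusion.** The concern holds in this form: the plan promises a time at which acute effects are gone and gives only a test against Hour 1, with no contrast, margin or interval rule. Failure to reject cannot support that conclusion at any sample size. At 29 per arm or fewer it leaves open a residual of about 0.38 SD of the change (within arm) or 0.53 SD (against placebo), even when the estimate is zero. These half-widths rest only on n = 29, a 95% level and a single-hour t contrast. The miss rates rest additionally on an assumed residual, and in raw units on an assumed correlation, so they are a range and not a forecast. The point should be settled before unblinding; it does not touch the primary pain analysis.

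**What to change.** In SAP 4.2.4:

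1. From the planned arm-by-time model, with time as a factor, estimate the active-minus-placebo difference in change from Hour 1 at every drive, for both SDLP and coherence. Report each with its 95% CI.
2. Fix and justify a margin for each measure before unblinding.
3. Declare recovery at an hour only if the confidence limit in the direction of impairment (upper for SDLP, lower for coherence) lies within the margin at that hour and at any later drive before the second dose.
4. Otherwise report *recovery not shown*, and state that a non-significant test will not be taken as recovery.

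This needs no new data, only SAP wording and two justified margins. The price is fewer and later declared recovery times. At 29 per arm the rule has 80% power at a single hour only for a margin of about 0.74 SD of the change, and less when later drives must also pass. With a tighter margin, *recovery not shown* would be a common result even if recovery were complete. Only three post-dose drives (Hours 2, 3 and 5) precede the second dose, so any recovery time will be coarse. Because Hour 1 follows eight weeks of treatment, the result speaks only to that day's dose.
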